### **7.1.3. Patient-reported Outcomes**

The effect of namilumab on select PROs will be evaluated, see [Appendix 9](#) for examples. The PROs used in this study include:

- KSQ General Score and Sub-scores;
- FAS;
- SGA.

Subjects will complete these assessments via electronic tablet as per the times specified in the SOA ([Appendix 1](#)).

During the administration of the instruments, the subjects should be allowed to sit alone in a quiet environment to answer the survey questions. All specific PRO assessments during a visit should be conducted before any tests, procedures, or other consultations to prevent influencing the subject's perception. Site staff and subjects will be given information on the rationale for including PROs in the study and clear instructions on how to complete the instruments.

The staff at the study site/clinic should never help the subject choose an answer and must be neutral in their responses to the subject's questions. The clinic staff are not allowed to interpret or rephrase the questions to the subjects. After the subject has completed the instruments, study staff will collect the data and check for completeness only.

The procedures for administration of the PRO instruments will be highlighted at the site training at each Investigator meeting. Study-specific PRO training will be given to all site Investigators and staff to ensure consistent oversight and management of the PRO administration process to ensure the highest possible quality of data. It is critical that all site Investigators and staff understand the rationale for including PROs in the protocol and the manner in which PRO instruments should be collected.

#### **7.1.3.1. King's Sarcoidosis Questionnaire**

The King's Sarcoidosis Questionnaire ([KSQ](#)) is a modular, multi-organ health status measure for subjects with sarcoidosis for use in the clinic and the evaluation of therapies. The KSQ consists of 5 modules: General health status (10 items), Lung (6 items), Medication (3 items), Skin (3 items), and Eye (7 items). The General health status module is intended to be administered to all subjects with sarcoidosis. In addition to this, all subjects will also complete organ-specific modules if relevant to their condition. All subjects will complete General health, and Medication modules and self-select the Lung, Skin and Eye modules if they have relevant symptoms for these assessments ([Patel, 2013](#)).

#### **7.1.3.2. Fatigue Assessment Scale**

The Fatigue Assessment Scale ([FAS](#)) is a 10-item self-reported fatigue questionnaire. The reliability and validity of the FAS have been demonstrated in sarcoidosis subjects. Subjects indicate their responses on a 5-point scale (from 1 never to 5 always). Total scores on the FAS can therefore range from 10 to 50, with high scores indicating more fatigue. Changes from baseline can range therefore from -40 to +40 on follow-up ([Michielsen, 2004](#)).

#### **7.1.3.3. Subject Global Assessment**

The Subject Global Assessment ([SGA](#)) is a subject reported outcome instrument used to assess their overall perception of the frequency and severity of sarcoid symptoms. The SGA- also sometimes termed Patient Global Assessment or PGA, is a 5-point scale which can be completed in less than a minute. It is similar to the pain VAS scale, which has been widely adapted to clinical practice. Using a Likert scale; the Subject rates how he/she feels regarding their sarcoidosis in the previous 2 weeks prior to the Study visit based on the frequency and severity of their symptoms. The SGA is based on the PGA published by Baughman et al but has been modified to be in line with FDA's recommendations on collection of patient global assessments ([Baughman, 2016](#)).

#### **7.1.4. Other Reported Outcomes**

The effect of namilumab on other physician-reported outcomes ([Appendix 10](#)) will be evaluated. These physician-reported assessments will include:

- Modified Glucocorticoid Toxicity Index (mGTI).

A representative example of this assessment is included in [Appendix 10](#). Subjects will complete these assessments via electronic tablet as per the times specified in the SOA ([Appendix 1](#)).

#### **7.1.4.1. Modified Glucocorticoid Toxicity Index**

The mGTI is a composite measure of the changes in OCS toxicity measured at 3-month intervals across 11 domains and 23 items. For the purposes of this study, radiographic assessment of bone mineral density is not being performed; therefore, this item is not being assessed in the tool and the tool is termed “modified” for this study. The change in the total score is from -35 to +410 with the exclusion of bone mineral density.

The mGTI measures changes in OCS toxicity rather than the absolute GC toxicity in order to account for the effects of prior OCS therapy and the background rate of AEs. The mGTI will be completed at the timepoints specified in the SOA ([Appendix 1](#)) ([Miloslavsky, 2017](#)).

### **7.2. Safety Assessments**

Planned timepoints for all safety assessments are provided in the SOA ([Appendix 1](#)). Assessments for safety include vital signs, height, and weight, PEs, ECGs, clinical laboratory assessments, and AEs.

#### **7.2.1. Vital Signs, Height, and Body Weight**

##### **7.2.1.1. Vital Signs**

Vital signs (BP, heart rate, respirations, and temperature) will be measured after 5 minutes of rest, with the participant in a quiet setting without distractions (e.g., television, cell phones). Vital sign measurements should be taken prior to any blood collections taken during the visit.

BP and heart rate measurements should be assessed in a seated position with a completely automated device; however, manual techniques may be used if an automated device is not available.

For the Screening Visit only, BP may be repeated 2 additional times at least 5 minutes apart if the subject does not meet inclusion/exclusion criteria. An average of the three systolic and diastolic readings may then be used for inclusion determination and should be entered into the eCRF.

The same method (oral temperature preferred) for assessing temperature should be used at all visits for a particular participant.

##### **7.2.1.2. Height**

Standing height will be measured without shoes.

##### **7.2.1.3. Body Weight**

Body weight will be measured in kilograms using a scale with appropriate range and resolution, and it must be placed on a stable, flat surface. Subjects should remove their shoes and bulky layers of clothing (jacket/coat), so that only light street clothing remains. Subjects should also remove the contents of their pockets and remain still during the weight measurement.

### **7.2.2. Physical Examinations**

A complete PE will include, at a minimum, assessments of the head, ears, eyes, nose, mouth, skin, lymph nodes, and abdomen (liver and spleen), as well as the cardiovascular, respiratory, gastrointestinal, and neurological systems.

A brief (targeted) PE will include, at a minimum, assessments of general appearance, the skin, and the cardiovascular and respiratory systems, and assessment of any subject-reported symptoms.

Investigators should pay special attention to clinical signs related to previous serious illnesses.

PEs may be conducted by a physician, trained physician's assistant, or nurse practitioner as acceptable according to local regulations.

### **7.2.3. Electrocardiograms**

A single 12-lead ECG(s) will be obtained as outlined in the SOA ([Appendix 1](#)) using the study-specific ECG machine that automatically calculates the heart rate and measures PR, QRS, QT, and QTc intervals, and QRS complex. All scheduled ECGs should be performed after the participant has rested quietly for at least 10 minutes in a supine position and prior to any blood collections.

When triplicate ECGs are required (e.g., at Screening only if the initial QTcF is >480 msec or as outlined in [Section 4.4.2.5](#) to assess changes in QTcF or QT that exceed thresholds), 3 individual ECG tracings should be obtained as closely as possible in succession, but no more than 2 minutes apart, and averaged together to make a determination.

### **7.2.4. Chest Radiography**

A standard posterior-anterior and lateral chest x-ray should be performed at Screening as outlined in the SOA ([Appendix 1](#)). No study specific requirements based on x-ray are required for inclusion; however, subjects with abnormal radiographic findings inconsistent with the diagnosis of sarcoidosis or the subject's past medical history and that warrant further investigation should be excluded.

### **7.2.5. Spirometry**

Spirometry will be performed to determine the subject's FEV1, ppFEV1, FVC, ppFVC, FEV1/FVC, and pFEV1/FVC. The predicted spirometry values will be determined using the 2012 Global Lung Function Equations. Spirometry assessments shall be obtained at the visits designated in the SOA ([Appendix 1](#)). Spirometry will be conducted while the subject is in a seated position. Every attempt should be made to standardize the time of day that a subject undergoes lung function testing throughout the study, and it is preferable that the same trained individual performs the spirometry testing for a given subject. All Site Investigators performing spirometry testing must pass competency prior to subject testing.

Spirometry results will be captured on standardized spirometry software and equipment and will be electronically transmitted and reviewed by a central over-reading service. Spirometry tests will be performed on a centralized spirometry system (provided to all sites by a central spirometry vendor) configured to the requirements of the study and in accordance with American

Thoracic Society (ATS)/European Respiratory Society (ERS) guidelines. The quality of the tests will be reported back to the site Investigators. Within each spirometry session, it is required that subjects produce flow-volume loops of acceptable and repeatable quality, as per ATS/ERS recommendations. To obtain the highest FEV1 and the highest FVC a minimum of three acceptable FVC maneuvers must be performed (with a maximum of 8 efforts per session).

Spirometry sessions must be stopped if the subject becomes tired or breathless. The details of these procedures will be described in the study pulmonary testing manual provided by the spirometry vendor.

#### **7.2.6. Tuberculosis Screening**

Subjects will be screened for TB using an interferon gamma release assay (IGRA) as supplied by the central laboratory. IGRA will be tested during Screening. Site personnel should follow the processing and analyses steps as outlined by the central laboratory manual. Ensure incubation steps are followed as appropriate.

If results of the IGRA are indeterminant, the test may be repeated, and if a negative result is obtained, enrollment may proceed as normal if the subject is otherwise eligible. A positive test on repeat requires that a subject commence appropriate anti-TB therapy prior to randomization as noted in [Section 4.2](#). Subjects with repeat indeterminate IGRA results should have a different IGRA test, if available, and may be enrolled without anti-TB therapy after consultation with an infectious disease and/or pulmonary specialist (the Investigator may qualify as such a specialist) who determines that risk of infection is low (i.e., participant would be acceptable for immunosuppressant treatment without additional action or therapy). Such determination should be documented in the subject's source record.

#### **7.2.7. HIV and Hepatitis Screening**

During the study Screening period, all subjects will be screened for HIV antibody (HIVAb), hepatitis B (hepatitis B surface antigen [HBsAg], hepatitis B surface antibody [HBsAb], and hepatitis B core antibody [HBcAb] with reflex testing as applicable), and hepatitis C (hepatitis C virus antibody [HCVAb] with reflex testing as applicable). Subjects with serologic evidence of infection with HIV, hepatitis B, or hepatitis C must have an undetectable viral load by RT-PCR prior to randomization to be eligible.

Subjects with hepatitis B serology suggestive of prior vaccination (i.e., negative HBsAg, negative HBcAb and positive HBsAb) and provide documentation of hepatitis B virus vaccination will not require RT-PCR evaluation prior to randomization.

#### **7.2.8. Clinical Safety Laboratory Assessments**

See [Appendix 5](#) for the list of clinical laboratory tests to be performed for Screening and safety monitoring; see the SOA ([Appendix 1](#)) for the timing and frequency.

The Investigator must review the laboratory report, document this review, and record any clinically significant changes occurring during the study as an AE. The laboratory reports must be filed with the source documents. New York State investigators will be blinded to the screening anti-GM-CSF auto-antibody laboratory results due to New York State regulations. These results will be made available to the New York State sites at the end of the trial.

Abnormal laboratory findings associated with the underlying disease are not considered clinically significant unless judged by the Investigator to be more severe than expected for the participant's condition.

All laboratory tests with values considered clinically significantly abnormal during participation in the study or within approximately 4 weeks after the last dose of study drug should be repeated until the values return to normal or Baseline or are no longer considered clinically significant by the Investigator or Medical Monitor.

If clinically significant values do not return to normal/Baseline within a period of time judged reasonable by the Investigator, the etiology should be identified, and the Sponsor notified.

All protocol-required laboratory tests must be conducted in accordance with the laboratory manual and the SOA ([Appendix 1](#)).

If laboratory values from non-protocol-specified laboratory tests performed at the institution's local laboratory require a change in participant management or are considered clinically significant by the Investigator (e.g., SAE or AE or dose interruption/discontinuation), then the results must be recorded.

### **7.2.9. Cytokine and Chemokine Analyses**

The following will be tested according to the SOA ([Appendix 1](#)) using a commercially available testing panel: GM-CSF; IL-1 $\alpha$ ; IL-5; IL-7; IL-12/IL-23p40; IL-15; IL-16; IL-17A; TNF- $\beta$ ; vascular endothelial growth factor; Interferon gamma (IFN- $\gamma$ ); IL-10; IL-12(p70); IL-13; IL-1 $\beta$ ; IL-2; IL-4; IL-6; IL-8; TNF- $\alpha$ ; Eotaxin, MIP-1 $\beta$ , Eotaxin-3, thymus activation regulated chemokine (TARC), MIP-1 $\alpha$ , Monocyte Chemoattractant Protein (MCP)-1, Macrophage Derived Chemokine (MDC), MCP-4, and 2 CXC (homeostatic) chemokine assays (IP-10, IL-8) (see [Appendix 5](#)).

### **7.2.10. Sarcoidosis Biomarkers**

The following will be tested according to the SOA ([Appendix 1](#)): soluble IL-2 receptor, and serum amyloid A with the inflammatory markers high-sensitivity CRP and erythrocyte sedimentation rate (ESR). A sample will be taken on the same sampling schedule for storage to assess at a future timepoint for additional biomarkers.

### **7.2.11. Sample Requirements**

The maximum amount of blood ([Table 6](#)) collected from each subject over the duration of the study, including any extra assessments that may be required, will be approximately 250 mL. Repeat or unscheduled samples may be taken for safety reasons or for technical issues with the samples.

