## 7. STUDY ASSESSMENTS AND PROCEDURES

Study procedures and their timing are summarized in the SOA ([Appendix 1](#)). As protocol waivers or exemptions are not allowed, except for immediate safety concerns, these should be

discussed with the Sponsor immediately upon occurrence or awareness to determine if the subject should continue or discontinue the study drug. Adherence to the study design requirements, including those specified in the SOA, is essential and required for study conduct.

All Screening evaluations must be completed and reviewed to confirm that potential subjects meet all eligibility criteria. The Investigator will maintain a screening log to record details of all subjects screened and to confirm eligibility or record reasons for screening failure ([Section 4.4.1](#)), as applicable. Procedures conducted as part of the subject's routine clinical management (e.g., blood count) and obtained before signing the ICF may be utilized for Screening or Baseline purposes provided the procedure met the protocol-specified criteria and was performed within the timeframe defined in the SOA.

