**Table 6. Estimated Sample Requirements Per Subject**

	Approximate sample volume per collection (mL)	Number of collection timepoints	Approximate total volume collected (mL)
Clinical laboratory tests	16.5	11	181.5
QuantiFERON® Gold/IGRA	11	1	11
Anti-GM-CSF autoantibody	2	1	2
PK	4	5	20
ADA	4	3	12
Cytokine and chemokine panel	8.5	5	42.5
SP-D, SAA, and biomarkers	5	5	25
FSH (if necessary)	3.5	1	3.5
Virology labs (hepatitis B, hepatitis C, and HIV)	5	1	5
Total:			302.5

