Serious adverse event monitoring m	X	X	X	X	X	X	X	X	X	X	X	X	X	X	X	X	X	

Schedule of Assessments																		
Study Period	Screen	Treatment Period																📞 FU a
Visit # (V)	V1	Baseline V2	V3	📞 V4-6 a	V7	📞 V8-10 a	V11	📞 V12-14 a	V15	📞 V16-18 a	V19	📞 V20-22 a	V23	V24	V25	EOT/ ET b V26	EOS FU c V27	
Week (W)	W -6	W0	W2	W3-5	W6	W7-9	W10	W11-13	W14	W15-17	W18	W19-21	W22	W26	W30	W34	W38	
Study Day (D) [Window based on Day 1 Visit]	D -42 to -1	D1	D15 [±3]	D22, D29, & D36 [±3]	D43 [±3]	D50, D57, & D64 [±3]	D71 [±3]	D78, D85, & D92 [±3]	D99 [±3]	D106, D113, & D120 [±3]	D127 [±3]	D134, D141, & D148 [±3]	D155 [±3]	D183 [±3]	D211 [±3]	D238 [±3]	295 [±7]	
Adverse event monitoring m		X	X	X	X	X	X	X	X	X	X	X	X	X	X	X	X	
TB test	X																	
Viral screen (Hep B, Hep C, HIV)	X																	
FSH (women only & if indicated) n	X																	
Sample for anti GM-CSF autoAb q	X																	
Sample for ADA (antibodies to namilumab) o		X								X							X	
Cytokine and chemokine samples		X					X		X					X		X		
Samples for hsCRP, SAA, sarcoid biomarkers, and SP-D measurement		X					X		X					X		X		

Schedule of Assessments																		
Study Period	Screen	Treatment Period																FU a
		Baseline	V2	V3	V4-6 a	V7	V8-10 a	V11	V12-14 a	V15	V16-18 a	V19	V20-22 a	V23	V24	V25	EOT/ ET b	EOS FU c
Visit # (V)	V1	V2	V3	V4-6 a	V7	V8-10 a	V11	V12-14 a	V15	V16-18 a	V19	V20-22 a	V23	V24	V25	V26	V27	
Week (W)	W -6	W0	W2	W3-5	W6	W7-9	W10	W11-13	W14	W15-17	W18	W19-21	W22	W26	W30	W34	W38	
Study Day (D) [Window based on Day 1 Visit]	D -42 to -1	D1	D15 [±3]	D22, D29, & D36 [±3]	D43 [±3]	D50, D57, & D64 [±3]	D71 [±3]	D78, D85, & D92 [±3]	D99 [±3]	D106, D113, & D120 [±3]	D127 [±3]	D134, D141, & D148 [±3]	D155 [±3]	D183 [±3]	D211 [±3]	D238 [±3]	295 [±7]	
Clinical laboratory: hematology	X	X	X		X		X		X		X		X	X	X	X		
Clinical laboratory: blood chemistry	X	X	X		X		X		X		X		X	X	X	X		
Clinical laboratory: urinalysis	X	X	X		X		X		X		X		X	X	X	X		
HbA 1C		X					X							X			X	
Vitamin D		X					X							X			X	
NT-proBNP		X					X							X			X	
Troponin		X					X							X			X	
Urine pregnancy test β-hCG (WCBP only)	X	X					X							X			X	
PK sample p			X		X				X					X		X		

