- j. Only central imaging interpretation will be accepted for eligibility determination. Scans conducted as part of the usual clinical management of the subject within 2 weeks prior to informed consent may be considered/assessed for use in place of the Screening PET/CT scan if the scans can be uploaded to central imaging vendor for central read and the OCS dose has not changed in the 4 weeks prior to the scan. Refer to [Section 7.1.2.1](#) for details
- k. Document whether the patient has completed taper by the specified timepoints described in [Appendix 8](#) or whether a dose increase/maintenance was needed. See [Section 6.4](#) for more details regarding rescue therapy. Patients should record OCS dose daily on provided eDiary.
- l. Collect information on concomitant medications and concurrent procedures from the time of informed consent through the EOS Visit, including prescription medications, over-the-counter medications, and herbal supplements/vitamins. All medications and procedures prior to randomization should be listed in the subject's medical history.
- m. All serious adverse events will be monitored and collected from the time of informed consent through the 8 weeks (56 day) post last dose of study drug FU. All adverse events will be monitored and collected from the time of randomization through the 8 weeks (56 day) post last dose of study drug FU. Treatment-emergent adverse events will be those that start or change in severity after the first dose of study drug.
- n. If necessary, follicle-stimulating hormone will be measured at Screening to confirm postmenopausal status.
- o. The ADA samples will be collected at Baseline (prior to the first dose) of Day 1 (Week 0), at Week 14, and at EOT. For subjects who terminate the study early, one ADA sample will be collected before discharging, when possible. Actual sampling time will be recorded.
- p. The PK samples will be collected prior to study drug administration at the appropriate timepoints and actual sampling time will be recorded.
- q. Investigators in the state of New York will remain blinded to the anti-GMCSF auto-antibody assay results until the end of the trial due to regulations within the state of New York.

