## APPENDIX 6. REGULATORY, ETHICAL, AND STUDY OVERSIGHT CONSIDERATIONS

### Regulatory and Ethical Considerations

This study will be conducted in accordance with the protocol and with the following:

- Consensus ethical principles derived from international guidelines including the Declaration of Helsinki and Council for International Organizations of Medical Sciences International Ethical Guidelines;
- Applicable ICH GCP Guidelines;
- Applicable laws and regulations.

The protocol, protocol amendments, ICF, Investigator's Brochure, and other relevant documents (e.g., advertisements) must be submitted to an IRB by the Investigator and reviewed and approved by the IRB before the study is initiated.

- Any amendments to the protocol will require IRB approval before implementation of changes made to the study design, except for changes necessary to eliminate an immediate hazard to study subjects.

The Investigator will be responsible for the following:

- Providing written summaries of the status of the study to the IRB annually or more frequently in accordance with the requirements, policies, and procedures established by the IRB;
- Notifying the IRB of SAEs or other significant safety findings as required by IRB procedures;
- Providing oversight of the conduct of the study at the site and adherence to requirements of 21 CFR, ICH guidelines, the IRB, and all other applicable local regulations.

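### Section 7.2.11 caps blood collection at about 250 mL per subject, but the table it cites correctly totals 302.5 mL (299.0 mL without the conditional FSH sample)

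*Combined protocol and SAP*

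**What the plan says.** Section 7.2.11 (Sample Requirements) gives a ceiling for blood drawn from one subject. The maximum "collected from each subject over the duration of the study, including any extra assessments that may be required, will be approximately 250 mL", and the same sentence points to Table 6. The next sentence adds: "Repeat or unscheduled samples may be taken for safety reasons or for technical issues with the samples". It does not say whether those samples fall inside the ceiling, and it gives no volume for them.

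Table 6 follows directly. It lists nine sample types with an approximate volume per collection, a number of collections and a row total, and it ends in a total of 302.5 mL. One row, FSH, is marked as conditional.

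The Schedule of Assessments in Appendix 1 shows when each sample is taken. It has rows such as "Clinical laboratory: hematology" and "Cytokine and chemokine samples", and a footnote fixes the anti-drug antibody draws: "The ADA samples will be collected at Baseline (prior to the first dose) of Day 1 (Week 0), at Week 14, and at EOT".

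**The concern.** The sentence and the table that it cites give different figures for the same quantity, and the sentence has the lower one. It is worded as a maximum that already covers extras, so it should be at least as large as the scheduled total. It is about 50 mL smaller.

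What is at stake is the accuracy of a participant-burden statement. Appendix 6 says that the protocol and consent form "must be submitted to an IRB by the Investigator and reviewed and approved by the IRB before the study is initiated". An IRB or site that relies on the sentence would take the burden to be lower than the protocol's own table shows.

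**Working it through.** **Inputs.** Volumes and counts come from Table 6. The last column is the number of marks in the matching row of the Schedule of Assessments (Appendix 1).

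| Sample | mL per draw | Draws (Table 6) | Product (mL) | Marks in schedule |
|---|---|---|---|---|
| Clinical laboratory tests | 16.5 | 11 | 181.5 | 11 |
| IGRA | 11 | 1 | 11 | 1 |
| Anti-GM-CSF autoantibody | 2 | 1 | 2 | 1 |
| PK | 4 | 5 | 20 | 5 |
| ADA | 4 | 3 | 12 | 3 |
| Cytokines and chemokines | 8.5 | 5 | 42.5 | 5 |
| SP-D, SAA, biomarkers | 5 | 5 | 25 | 5 |
| FSH (conditional) | 3.5 | 1 | 3.5 | 1 |
| Virology | 5 | 1 | 5 | 1 |

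**Step 1: reproduce the table's total.** Total = sum of (volume per draw × number of draws) = 181.5 + 11 + 2 + 20 + 12 + 42.5 + 25 + 3.5 + 5 = 302.5 mL. Every row product and the total agree with Table 6.

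**Step 2: remove the conditional row.** 302.5 − 3.5 = 299.0 mL.

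**Step 3: compare with the stated maximum.**
- With FSH: 302.5 − 250 = 52.5 mL; 52.5 / 250 = 21.0%.
- Without FSH: 299.0 − 250 = 49.0 mL; 49.0 / 250 = 19.6%.

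**Step 4: check the counts.** The 11 clinical laboratory draws are the hematology and chemistry marks at Screening, Baseline and Weeks 2, 6, 10, 14, 18, 22, 26, 30 and 34. The other rows also match, so Table 6 does not overcount visits.

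**Step 5: look for a reading that gives 250 mL.**
- Sections 7.4 and 7.5 tie the PK and ADA samples to subjects who have received namilumab. Leaving out both gives 302.5 − 20 − 12 = 270.5 mL, which is 20.5 mL (8.2%) over. Without FSH as well it is 267.0 mL, which is 17.0 mL (6.8%) over. A maximum has to cover namilumab recipients in any case.
- Eight clinical laboratory draws instead of 11 would give 302.5 − 3 × 16.5 = 253.0 mL, or 249.5 mL without FSH. The schedule shows 11.
- Some combinations of omitted rows also come close, such as IGRA with the cytokine panel: 302.5 − 11 − 42.5 = 249.0 mL. Nothing in the documents supports leaving those rows out.

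**Step 6: what this check cannot settle.** The schedule gives times but no volumes, so it supports the counts and not the volume per draw. It also marks HbA1c, vitamin D, NT-proBNP and troponin four times each, and none of these has its own row in Table 6. Whether they are inside the 16.5 mL clinical laboratory draw is not stated.

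**The case against.** The strongest reply is that the documents show a mismatch without proving which number is wrong. Matching counts say nothing about volumes, and one volume carries most of the total: 181.5 / 302.5 = 60% rests on the 16.5 mL clinical laboratory draw. At 12 mL, to take an illustrative value, that row would be 132 mL and the total 302.5 − 181.5 + 132 = 253.0 mL. The coverage of the table is also unclear. If the four tests without a row are inside the 16.5 mL, using that volume at all 11 visits may overstate the total. If they are outside it, the table understates the total. SP-D and high-sensitivity CRP add to the doubt: Appendix 5 lists both under blood chemistry, while Table 6 puts SP-D, and the schedule puts both, with the biomarker samples.

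Part of this stands. A reader might infer that the schedule check proves every volume in Table 6; it does not, so the volumes should be confirmed before a new figure is written in. But no document supports 12 mL. The figures that are given add to 302.5 mL, and the sentence names that table as its source.

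A second reply is that the word for an approximate figure absorbs the gap, and that Table 6 is itself an estimate. An excess of 20 to 21% over a stated maximum is not rounding: 302.5 rounds to about 300.

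A reader might also infer that every subject will have more than 250 mL drawn. The documents do not support that. Under Section 7, routine procedures done before consent "may be utilized for Screening or Baseline purposes provided the procedure met the protocol-specified criteria" and are done in time, so an individual total can be lower. That does not help a maximum, which must cover a subject whose samples are all drawn in the study.

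Nor can it be said that participants were told the wrong figure, because the consent form was not available. Nor do the documents set a blood-volume limit that either figure breaches. The difference is about 50 mL over roughly 44 weeks, and the table sits directly below the sentence, so the practical weight is modest.

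**Conclusion.** The inconsistency is real, and no reading supported by the documents removes it. The stated maximum of about 250 mL is 52.5 mL (21.0%) below the total of the table it cites, or 49.0 mL (19.6%) below it without FSH. Both comparisons are before any repeat or unscheduled draw.

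The conclusion that the sentence is the figure to change rests on two things: the table's arithmetic is correct, and its counts match the schedule. It assumes that the listed volumes per draw are right and that they cover the four tests without a row. Confidence is high that the two figures conflict and lower that 302.5 mL is exact.

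The effect is confined to the burden figure that the IRB and sites see. No endpoint, sample size or analysis is touched. It should be corrected because the correction is specific and nearly free.

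**What to change.** 1. Confirm the Table 6 volumes per draw against the laboratory manual, and settle whether HbA1c, vitamin D, NT-proBNP and troponin are inside the listed volumes. Amend the table if they are not.
2. In Section 7.2.11, replace the 250 mL figure with the Table 6 total. As the table stands, that is about 300 mL (302.5 mL with FSH).
3. State in the same section that repeat or unscheduled samples are additional to this figure.
4. If the consent form repeats 250 mL, align it.

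The cost is one check against the manual, one changed number and one added sentence, and a consent edit if needed. The stated burden becomes slightly less favourable. No visit, procedure, endpoint or analysis changes.
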